- y At Week 14, subjects who failed to achieve both a TJC and SJC improvement of $\geq 20\%$ will be treated as inadequate responders and discontinue study drugs but will continue with study visits and assessments
- z Subjects on placebo will be switched from placebo to filgotinib at Week 24
- aa Subjects failing to maintain at least a 20% improvement from Day 1 in TJC and SJC confirmed at 2 consecutive visits will discontinue study drugs but will continue with study visits and assessments
- bb Dispensation of study drug(s) according to IWRS manual
- cc Self-injection or caregiver training will occur at Day 1. This can be repeated at Week 2 as required.

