3.8. Analysis Visit Windows

3.8.1. Definition of Study Day

The first dose date of individual study drug will be calculated separately for each study drug (ie, filgotinib 200mg, filgotinib 100mg, adalimumab and PTMs) in a treatment group. Study Day 1 is defined as the first dose date of any study drug, which is the minimum of the first dose dates of individual study drugs in a treatment group.

The last dose date of individual study drug will be calculated separately for each study drug in a treatment group. The last dose date for an individual study drug will be the end date on study drug administration CRF for the record where the “study drug was permanently withdrawn” flag is “Yes”. The last dose date of any study drug will be defined as the maximum of the last dose dates of individual study drugs in a treatment group.

Study Day will be calculated from the Study Day 1 and derived as follows:

- For postdose study days: Assessment Date – Study Day 1 + 1
- For days prior to the first dose: Assessment Date – Study Day 1

For subjects who were on placebo and then re-randomized, the On-Filgotinib Study Day 1 is defined as the first dose date of filgotinib which is identified by the first dispense date of filgotinib. The On-Filgotinib Study Day will be calculated from the On-Filgotinib Study Day 1 and derived as follows:

- For postdose study days of filgotinib: Assessment Date – On-Filgotinib Study Day 1 + 1
- For days prior to the first dose of filgotinib: Assessment Date – On-Filgotinib Study Day 1

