Table 3-1. Analysis Visit Windows for On-Treatment Joint Count Assessment, HAQ-DI, SGA, PGA, CRP, Exploratory PRO, and Vital Signs, Weight, and Safety Laboratory Data (Lipid Data Excluded) for Subjects who were Initially Randomized to Filgotinib or Adalimumab, and Subjects who were Initially Randomized to Placebo and not Re-randomized

Analysis Visit	Nominal Study Day	Lower Limit	Upper Limit
Baseline	1	(none)	1
Week 2	15	2	22
Week 4	29	23	43
Week 8	57	44	71
Week 12	85	72	92
Week 14	99	93	106
Week 16	113	107	127
Week 20	141	128	155
Week 24	169	156	176
Week 26	183	177	197
Week 30	211	198	232
Week 36	253	233	281
Week 44	309	282	337
Week 52	365	338	≥ 365

Table 3-2. Analysis Visit Windows for On-Treatment Joint Count Assessment, HAQ-DI, SGA, PGA, CRP, Exploratory PRO, and Vital Signs, Weight, and Safety Laboratory Data (Lipid Data Excluded) for Subjects who were Initially Randomized to Placebo and Re-randomized

Analysis Visit	Nominal Study Day	Lower Limit	Upper Limit
Baseline	1	(none)	1
Week 2	15	2	22
Week 4	29	23	43
Week 8	57	44	71
Week 12	85	72	92
Week 14	99	93	106
Week 16	113	107	127
Week 20	141	128	155
Week 24	169	156	First Dose Date of Filgotinib - Study Day 1 + 1
Analysis Visit	On-Filgotinib Study Day	On-Filgotinib Lower Limit	On-Filgotinib Upper Limit
Week 26*	15	2	29
Week 30*	43	30	64
Week 36*	85	65	113
Week 44*	141	114	169
Week 52*	197	170	≥ 197

* For subjects who were on placebo and re-randomized their analysis window after Week 24 will be assigned according to On-Filgotinib Study Day, On-Filgotinib Lower Limit and On-Filgotinib Upper Limit.

The analysis windows for on-treatment mTSS and lipid data are provided in [Table 3-3](#), [Table 3-4](#), [Table 3-5](#), and [Table 3-6](#).

Table 3-3. Analysis Visit Windows for On-Treatment Lipid Data for Subjects who were Initially Randomized to Filgotinib or Adalimumab, and Subjects who were Initially Randomized to Placebo and not Re-randomized

Analysis Visit	Nominal Study Day	Lower Limit	Upper Limit
Baseline	1	(none)	1
Week 12	85	2	127
Week 24	169	128	267
Week 52	365	268	≥ 365

Table 3-4. Analysis Visit Windows for On-Treatment mTSS for Subjects who were Initially Randomized to Filgotinib or Adalimumab, and Subjects who were Initially Randomized to Placebo and not Re-randomized

Analysis Visit	Nominal Study Day	Lower Limit	Upper Limit
Baseline	1	(none)	15
Week 12	85	16	127
Week 24	169	128	267
Week 52	365	268	≥ 365

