- Last observation carried forward (LOCF): Baseline measurements will not be carried forward to postbaseline. Only postbaseline measurements will be LOCF. For the composite endpoints, the last nonmissing postbaseline observation will be carried forward to subsequent visits for each individual component first, and then calculate the composite endpoints using individual components imputed by LOCF as described above. If a subject does not have a nonmissing observed record for a postbaseline visit, the last postbaseline record prior to the missed visit will be used for this postbaseline visit. If the last nonmissing observation prior to the missing visits cannot be determined due to multiple measurements occurring at the same time or the time not available within the same day, the worst outcome will be used for LOCF. If missing components still exist after LOCF, the composite endpoints will be calculated using the same rules as described in OC.
- Non-responder imputation (NRI): For all binary response measurements, starting from OC, all missings will be set as non-responders.

If a subject only has baseline measurements, LOCF and OC analyses will not include this subject. But this subject will be treated as non-responder in NRI analyses.

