6.4.2. Analysis Methods for Other Secondary Efficacy Endpoints

The FAS will be used for all summaries and analyses of other secondary efficacy endpoints. Statistical testing will be performed up to Week 24. The nominal p-values will be presented, if applicable. No formal statistical testing will be performed after Week 24, unless otherwise specified.

The proportion of subjects who achieve ACR20/50/70, and proportion of subjects with change in HAQ-DI ≥ 0.22 (ie, reduction in HAQ-DI ≥ 0.22), DAS28(CRP) ≤ 3.2 or DAS28(CRP) < 2.6 , will be analyzed using the same logistic regression method with NRI as the primary endpoint analysis described in Section 6.2.3. Comparison will be made between each filgotinib dose group and placebo group. The 2-sided 95% CIs for the proportion based on normal approximation with the sample variance will be provided for each treatment group and visit. In addition, non-stratified response rate difference along with its 95% CI calculated based on the normal approximation with the pooled sample variance will be provided. The OC and LOCF values will be analyzed as a sensitivity approach to the primary method that uses NRI.

The proportion of subjects having no radiographic progression as defined by change from baseline in mTSS ≤ 0.5 at Week 24 will be analyzed using the same logistic regression method based on the OC. Comparison will be made between each filgotinib dose group and placebo group. The 2 sided 95% CIs for the proportion based on normal approximation with the sample variance will be provided for each treatment group. In addition, non-stratified response rate difference along with its 95% CI calculated based on the normal approximation with the pooled sample variance will be provided. The no radiographic progression as defined by change from baseline in mTSS ≤ 0 , and the smallest detectable change (SDC) at Week 24 will also be analyzed using the logistic regression method based on the OC. SDC is the smallest detectable change computed from the variability in change from baseline in mTSS of the two imaging assessors {Bruynesteyn 2005}.

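### A Week 24 visit after Day 176 stays Week 24 for re-randomized placebo subjects but becomes Week 26, and usually non-response under NRI, for everyone else

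*SAP*

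**What the plan says.** SAP Section 3.8.2 assigns observations to visits by study day, using two tables for joint counts, HAQ-DI, SGA, PGA and CRP.

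- Table 3-1 covers "Subjects who were Initially Randomized to Filgotinib or Adalimumab, and Subjects who were Initially Randomized to Placebo and not Re-randomized". Its Week 24 row (nominal day, lower limit, upper limit) is "Week 24 169 156 176", and the next row is "Week 26 183 177 197".
- Table 3-2 covers placebo subjects who are re-randomized. Week 24 again opens on Day 156, but its upper limit is "First Dose Date of Filgotinib - Study Day 1 + 1", with no calendar cap.

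Section 3.8.1 defines the start of filgotinib in these subjects as "the first dose date of filgotinib which is identified by the first dispense date of filgotinib". Protocol Appendix 2 states: "Subjects on placebo will be switched from placebo to filgotinib at Week 24".

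Under SAP Section 6.1, components are placed in windows before a composite is derived. If several records share a window, the one closest to the nominal day is used. For NRI, "starting from OC, all missings will be set as non-responders".

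Section 6.4.2 says of the other secondary endpoints: "Statistical testing will be performed up to Week 24". The p-values there are nominal, and OC and LOCF analyses accompany NRI for the main binary endpoints.

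**The concern.** In a randomized comparison, the rule that decides whether a visit counts should not depend on the assigned arm. Here it does. The placebo limit follows the visit itself, because the switch date is the dispense date and dispensing happens at the Week 24 visit. The active-arm limit is a fixed day. Section 3.8.2 has no rule that keeps a nominal Week 24 visit in Week 24 when it falls after Day 176, although Section 6.1 uses nominal visits for the Week 14 non-responder rule.

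At stake are the Week 24 filgotinib-placebo comparisons of ACR20/50/70, DAS28(CRP) ≤ 3.2 and < 2.6, and HAQ-DI reduction ≥ 0.22 (Section 6.4.2), and the Week 24 subgroup analyses of ACR20 (Section 6.2.5) and DAS28(CRP) < 2.6 (Section 6.3.4). Among the MMRM endpoints, HAQ-DI, DAS28(CRP), CDAI, SDAI and the ACR components would lose the Week 24 value but would not be scored as failures.

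**Working it through.** **1. Reproduce the limit.** Table 3-1 sets upper limits at the midpoint of adjacent nominal days. For Week 24, (169 + 183)/2 = 176, as printed. All 12 upper limits from Week 2 to Week 44 reproduce this way. The Week 24 limit in Table 3-2 follows a different logic, the date of the switch.

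**2. Classify a late visit.** The Table 3-2 column takes the visit as the dispense day.

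| Day of Week 24 visit | Table 3-1 | Table 3-2 |
|---|---|---|
| 172 (end of the protocol's ±3 days) | Week 24 | Week 24 |
| 176 | Week 24 | Week 24 |
| 177 | Week 26 | Week 24 |
| 180 | Week 26 | Week 24 |
| 190 | Week 26 | Week 24 |

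The tables part at Day 177, which is 8 days after nominal Day 169 and 5 days beyond the protocol tolerance.

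**3. Knock-on at Week 26.** A displaced record competes for the Week 26 window. A Week 24 visit on Day 181 is 2 days from Day 183; a true Week 26 visit on Day 186 is 3 days away. The Week 24 record would be chosen.

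**4. Size under NRI.** Let q be the share of Week 24 visits after Day 176, p_A the active Week 24 response rate and p_P the placebo rate. As written, the difference becomes p_A(1 − q) − p_P, so the loss is q × p_A.

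Rates are the Week 24 ACR20 rates in protocol Table 1-1 (Phase 2b, once daily with MTX), used only for scale: 73.3% for 200 mg, 61.2% for 100 mg and 41.9% for placebo. The differences without late visits are 31.4 and 19.3 points. The documents do not give q, so the range is assumed.

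| q | 200 mg loss | 200 mg difference | 100 mg loss | 100 mg difference |
|---|---|---|---|---|
| 0.5% | 0.37 | 31.0 | 0.31 | 19.0 |
| 1% | 0.73 | 30.7 | 0.61 | 18.7 |
| 2% | 1.47 | 29.9 | 1.22 | 18.1 |
| 3% | 2.20 | 29.2 | 1.84 | 17.5 |

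The standard error of the 200 mg difference at 450 per arm is sqrt(0.733 × 0.267/450 + 0.419 × 0.581/450) = 3.1 points.

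**5. What is not reached.**

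- The Week 12 window is Days 72-92 in both tables, so the primary endpoint and the Week 12 tests built on them are untouched.
- mTSS is the only Week 24 endpoint in the Section 3.5 hierarchy. Its Week 24 window runs to Day 267 in the active arms (Table 3-4), and it is analysed by MMRM.
- For SF-36, FACIT-Fatigue and EQ-5D the active-arm Week 24 window runs to Day 211 (Table 3-9), so a Day 180 visit stays in Week 24.
- Filgotinib and adalimumab both follow Table 3-1, so their comparison is not distorted by the table difference.

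**The case against.** The best defence is that the design forces the difference. Placebo data must stop at the switch, Day 176 is the ordinary midpoint, and a Day 180 record is nearer Day 183 (3 days) than Day 169 (11 days). That explains why Table 3-2 ends where it does. It does not explain why the same scheduled visit should count in one arm and not in another.

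Other points on this side stand:

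- The affected tests are nominal or subgroup analyses, and the bias runs against filgotinib, so it is conservative for superiority.
- Section 6.4.2 plans OC and LOCF for the main binary endpoints. OC drops a displaced subject and LOCF carries the previous post-baseline value forward, so neither scores lateness as failure. The subgroup analyses are specified with NRI only.
- Exposure requires a visit well outside the protocol tolerance, so late visits may be few.
- The tables can also differ in the other direction. A repeat assessment two days after an on-time placebo visit falls in Week 26, whereas in an active arm it counts for Week 24 up to Day 176.

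A reader might infer that only the active arms pay for lateness. The documents do not support that: placebo subjects who are not re-randomized also follow Table 3-1. In the on-treatment dataset most of them should be off drug and already missing at Week 24. In the all-available-data analysis, where Section 3.8.2 applies the same windows under standard of care, a late visit costs them a response too. Nor do the documents support a claim that every MMRM endpoint loses its Week 24 value in the active arms, given the wider windows listed above.

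**Conclusion.** The inconsistency is real and follows from the text, but it is minor. A Week 24 visit after Day 176 is scored as observed in re-randomized placebo. In both filgotinib arms, adalimumab and placebo subjects not re-randomized, it is scored as non-response under NRI unless another record lies in Days 156-176.

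For 200 mg ACR20 the loss is about 0.7 points per 1% of late visits, or 0.4 to 2.2 points over the assumed range. That is below one standard error on a difference of about 31 points, so no overall conclusion would be expected to change. It is still a systematic error in reported effect sizes that a larger sample would not reduce.

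The figures assume an equal late share in all arms, lateness unrelated to response, no second record in the window, Phase 2b response rates, and that every placebo subject with a Week 24 response is re-randomized. In the all-available-data analysis the bias would be smaller to the extent that placebo responders are not re-randomized.

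**What to change.** In Table 3-1, set the Week 24 upper limit to the later of Day 176 and the date of the nominal Week 24 visit, and start Week 26 on the following day. The Week 24 visit then counts as Week 24 in every arm, and under the assumptions above the 200 mg difference returns to 31.4 points at any late share.

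Do not instead cap Table 3-2 at Day 176. A placebo visit on a dispense day after Day 176 is On-Filgotinib Day 1, while the Week 26 window opens on On-Filgotinib Day 2, so the record would fall in no window. The cap would also leave some bias: at a 1% late share the difference would be 31.4 × 0.99 = 31.1 points.

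The cost is one table row, reprogramming of the window derivation, and a visit-label rule for a single visit in a scheme otherwise based on study day. Week 24 windows would still close earlier for re-randomized placebo after an on-time visit, which the switch makes unavoidable. The SAP is to be finalized before the Week 24 unblinding, and the edit belongs before that point. If it comes later, Section 1 requires it to be documented in the CSR.

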Table 3-5. Analysis Visit Windows for On-Treatment Lipid Data for Subjects who were Initially Randomized to Placebo and Re-randomized

Analysis Visit	Nominal Study Day	Lower Limit	Upper Limit
Baseline	1	(none)	1
Week 12	85	2	127
Week 24	169	128	First Dose Date of Filgotinib - Study Day 1 + 1
Analysis Visit	On-Filgotinib Study Day	On-Filgotinib Lower Limit	On-Filgotinib Upper Limit
Week 52*	197	2	≥ 197

* For subjects who were on placebo and re-randomized their analysis window after Week 24 will be assigned according to On-Filgotinib Study Day, On-Filgotinib Lower Limit and On-Filgotinib Upper Limit.

Table 3-6. Analysis Visit Windows for On-Treatment mTSS data for Subjects who were Initially Randomized to Placebo and Re-randomized

Analysis Visit	Nominal Study Day	Lower Limit	Upper Limit
Baseline	1	(none)	15
Week 12	85	16	127
Week 24	169	128	(First Dose Date of Filgotinib + 14) - Study Day 1 + 1
Analysis Visit	On-Filgotinib Study Day	On-Filgotinib Lower Limit	On-Filgotinib Upper Limit
Week 52*	197	16	≥ 197

* For subjects who were on placebo and re-randomized their analysis window after Week 24 will be assigned according to On-Filgotinib Study Day, On-Filgotinib Lower Limit and On-Filgotinib Upper Limit.

The analysis windows for On-Treatment Healthcare Resource Utilization Questionnaire (HRUQ), Treatment Satisfaction Questionnaire for Medication (TSQM) and ECG data are provided in [Table 3-7](#) and [Table 3-8](#).

Table 3-7. Analysis Visit Windows for On-Treatment HRUQ,TSQM and ECG Data for Subjects who were Initially Randomized to Filgotinib or Adalimumab, and Subjects who were Initially Randomized to Placebo and not Re-randomized

Analysis Visit	Nominal Study Day	Lower Limit	Upper Limit
Baseline	1	(none)	1
Week 12	85	2	127
Week 24	169	128	211
Week 36	253	212	309
Week 52	365	310	≥ 365

Table 3-8. Analysis Visit Windows for On-Treatment HRUQ,TSQM and ECG Data for Subjects who were Initially Randomized to Placebo and Re-randomized

Analysis Visit	Nominal Study Day	Lower Limit	Upper Limit
Baseline	1	(none)	1
Week 12	85	2	127
Week 24	169	128	First Dose Date of Filgotinib - Study Day 1 + 1
Analysis Visit	On-Filgotinib Study Day	On-Filgotinib Lower Limit	On-Filgotinib Upper Limit
Week 36*	85	2	141
Week 52*	197	142	≥ 197

* For subjects who were on placebo and re-randomized their analysis window after Week 24 will be assigned according to On-Filgotinib Study Day, On-Filgotinib Lower Limit and On-Filgotinib Upper Limit.

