The analysis windows for on-treatment SF-36, FACIT-Fatigue, EQ-5D and WPAI-RA are provided in [Table 3-9](#) and [Table 3-10](#).

Table 3-9. Analysis Visit Windows for On-Treatment SF-36, FACIT-Fatigue, EQ-5D, and WPAI-RA for Subjects who were Initially Randomized to Filgotinib or Adalimumab, and Subjects who were Initially Randomized to Placebo and not Re-randomized

Analysis Visit	Nominal Study Day	Lower Limit	Upper Limit
Baseline	1	(none)	1
Week 4	29	2	57
Week 12	85	58	127
Week 24	169	128	211
Week 36	253	212	309
Week 52	365	310	≥ 365

Table 3-10. Analysis Visit Windows for On-Treatment SF-36, FACIT-Fatigue, EQ-5D, and WPAI-RA for Subjects who were Initially Randomized to Placebo and Re-randomized

Analysis Visit	Nominal Study Day	Lower Limit	Upper Limit
Baseline	1	(none)	1
Week 4	29	2	57
Week 12	85	58	127
Week 24	169	128	First Dose Date of Filgotinib - Study Day 1 + 1
Analysis Visit	On-Filgotinib Study Day	On-Filgotinib Lower Limit	On-Filgotinib Upper Limit
Week 36*	85	2	141
Week 52*	197	142	≥ 197

* For subjects who were on placebo and re-randomized their analysis window after Week 24 will be assigned according to On-Filgotinib Study Day, On-Filgotinib Lower Limit and On-Filgotinib Upper Limit.

Vital signs, weight, ECG, lipids and safety laboratory data collected in the post-treatment follow-up period will also be summarized. The analysis window for the post-treatment follow-up period is defined as from (the last dose date of any study drug + 8 days) to (the last dose date of any study drug + 30 days). If multiple valid, nonmissing measurements exist in the post-treatment follow-up visit window, then the latest record will be selected for analysis. If the chronological order cannot be determined (eg, more than 1 record on the same day with time missing), for any given subject, the value with the worst severity will be selected for categorical variable, and the average will be taken for continuous variable. Data obtained after last dose date plus 30 days will be excluded from the summaries, but will be included in the listings.

For efficacy endpoints, the same analysis visit windows will be applied to all available data collected during standard of care.

3.8.3. Selection of Non-Efficacy Data in the Event of Multiple Records in an Analysis Visit Window

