Summary statistics of the actual scores and change from baseline in each of the four types of scores of WPAI-RA (absenteeism, presenteeism, work productivity loss, and activity impairment) will be summarized by treatment and visit using descriptive statistics (sample size, mean, SD, median, Q1, Q3, minimum and maximum).

The analyses of absenteeism, presenteeism, and work productivity loss will be based on subjects employed at both baseline and postbaseline visits.

- **HRUQ**

Summary statistics will be provided for all the following parameters by treatment group and visit.

Healthcare resource utilization – Outpatient visits:

— Number and percentage of subjects with any medical visits, and the number of visits related to RA will be provided for the categories:

- Outpatient Healthcare Provider
- Emergency Room
- Chiropractor, Physical or Occupational Therapist

Healthcare resource utilization – Inpatient hospitalization:

— Number and percentage of subject with hospital stays, and number of stays related to RA

— Descriptive statistics for the total number of days in hospital related to RA

— Number and percentage of subject with nursing home or rehabilitation center stays, and number of stays related to RA

— Descriptive statistics for the total number of days in nursing home or rehabilitation center related to RA

- **TSQM**

Descriptive statistics of the scores from each of the 4 domains (Effectiveness, Side Effects, Convenience, and Global Satisfaction) will be presented by treatment group and by visit.

- **Exploratory PRO**

CCI

Plots of proportions of subjects for categorical endpoints and mean \pm SD for continuous endpoints (including each individual component of the ACR response) will be presented over time by treatment.

Additional statistical tests will be performed for the following efficacy endpoints;

- Compare each filgotinib dose group with adalimumab group at week 24 and 52 in proportion of subjects achieving ACR20, $\text{DAS28(CRP)} \leq 3.2$ and $\text{DAS28(CRP)} < 2.6$ using similar logistic regression as described in Section 6.2.3, and in change from baseline in HAQ-DI, SF-36 PCS and FACIT-Fatigue using similar MMRM model as described in Section 6.3.2.

- Compare filgotinib 200 mg group with placebo switching to filgotinib 200 mg group, and filgotinib 100 mg group with placebo switching to filgotinib 100 mg group at Week 52 in change from baseline in mTSS using similar MMRM model as described in Section 6.3.2.

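### For lipids and mTSS, the Week 52 window of placebo switchers opens at On-Filgotinib Day 2 or Day 16, on calendar days that the continuous arms file as Week 24

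*SAP*

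**What the plan says.** SAP 3.8.1 defines two day counts. Study Day runs from the first dose of any study drug. For re-randomised placebo subjects, a second count, On-Filgotinib Study Day, starts at 1 on the first filgotinib dose. SAP 3.8.2 windows the switchers' later data on the second count: "their analysis window after Week 24 will be assigned according to On-Filgotinib Study Day, On-Filgotinib Lower Limit and On-Filgotinib Upper Limit".

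The rows that matter give nominal day, lower limit and upper limit, in that order:

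- Continuous filgotinib and adalimumab, and placebo subjects not re-randomised, Table 3-3 (lipids) and Table 3-4 (mTSS): "Week 24 169 128 267" and "Week 52 365 268 ≥ 365".
- Switchers, Table 3-6 (mTSS), on the On-Filgotinib count: "Week 52* 197 16 ≥ 197".
- Switchers, Table 3-5 (lipids), on the same count: "Week 52* 197 2 ≥ 197".

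Tables 3-5 and 3-6 have no other post-switch visit. If a window holds several records, the one nearest the nominal day is used (SAP 3.8.3 for safety data, 6.1 for efficacy). On-treatment data end 7 days after the last dose.

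Among the additional tests in SAP 6.4.2 is one at Week 52 on mTSS change: "Compare filgotinib 200 mg group with placebo switching to filgotinib 200 mg group", with the matching pair at 100 mg. The same pairs are compared on the proportion without radiographic progression. Lipids are summarised by group and visit (SAP 7.2.1).

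**The concern.** The groups set side by side at Week 52 do not share a definition of Week 52. For several weeks after the switch, a film or lipid sample taken on one calendar day is a Week 52 record in a switcher and a Week 24 record in a continuous-arm subject. In the continuous arm it usually also loses to the scheduled Week 24 record, which lies nearer Day 169, so it reaches neither row.

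The nearest-to-nominal rule protects anyone who has a later on-treatment record. The subjects affected are those who leave early. A switcher's early film then stands as a Week 52 outcome after little time for joint damage to progress, which would tend to flatter the switch group. An early lipid value may precede the plateau that the protocol describes for Phase 2b.

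**Working it through.** **Inputs.** Window limits from SAP Tables 3-1 to 3-10; day counts from SAP 3.8.1; film waiver from Protocol Appendix 2 (no early-termination film if one was taken less than 12 weeks before); visit window of ±3 days at Week 24 and ±7 days for radiographs (Protocol Appendix 2). Assumption: the switch falls on Study Day 169, the nominal Week 24 day.

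**1. Reproduce the SAP's own limits.** The continuous-arm boundary is a midpoint: (169 + 365)/2 = 267, so Week 24 ends on 267 and Week 52 starts on 268, as stated. The switchers' nominal Week 52 day is an offset: On-Filgotinib Day = Study Day − 168, and 365 − 168 = 197, as stated.

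**2. Apply the same offset to the lower limits.**

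| Table for switchers | Continuous-arm lower limit | Minus 168 | Stated |
|---|---|---|---|
| 3-2, Week 30 | 198 | 30 | 30 |
| 3-2, Week 36 | 233 | 65 | 65 |
| 3-2, Week 44 | 282 | 114 | 114 |
| 3-2, Week 52 | 338 | 170 | 170 |
| 3-8 and 3-10, Week 52 | 310 | 142 | 142 |
| 3-5, Week 52 (lipids) | 268 | 100 | 2 |
| 3-6, Week 52 (mTSS) | 268 | 100 | 16 |

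Week 52 follows the calendar in Tables 3-2, 3-8 and 3-10, and departs from it in Tables 3-5 and 3-6.

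**3. Length of the mismatch.** Study Day = On-Filgotinib Day + 168.

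- Films: Day 16 is Study Day 184. Labels differ on Study Days 184 to 267, which is 267 − 184 + 1 = 84 days.
- Lipids: Day 2 is Study Day 170. Labels differ on Study Days 170 to 267, which is 98 days.
- With the switch on Study Day 166 or 172, the counts are 87 or 81 days for films and 101 or 95 days for lipids.

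**4. Two example records.** A film on Study Day 255 is On-Filgotinib Day 87: Week 52 in a switcher, Week 24 in a continuous-arm subject. Fasting lipids at an exit on Study Day 178 are On-Filgotinib Day 10: Week 52 in a switcher, Week 24 in a continuous-arm subject.

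**5. How many films can be affected.** With a Week 24 film on Day 169, an early-termination film is required only from Day 169 + 84 = 253. Required films with differing labels therefore fall on Study Days 253 to 267, which is 15 days. If the Week 24 film was on Day 162 or 176, this becomes 22 or 8 days. Earlier films are possible but not required. Lipids have no such waiver: Protocol 6.5 lists a fasting lipid profile at every early-termination visit.

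**6. Where the mismatch ends.** From Study Day 268, about Week 38 (268/7 = 38.3), an early exit is Week 52 in every arm, up to 365 − 268 = 97 days before the nominal day.

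**The case against.** The best defence is that the limits follow a convention. SAP 3.8.2 gives switchers a new baseline at the first filgotinib dose (plus 14 days for mTSS), and the first window after a baseline commonly opens the next day: Week 12 opens on Day 2 in Table 3-3 and on Day 16 in Table 3-4. On this view Days 2 and 16 are deliberate. That explains the numbers. It does not cure the mismatch, because the initial windows treat all randomised groups alike, whereas here only one side of a planned comparison is re-windowed. In Table 3-2 the same convention is harmless: Week 26 opens on Day 2 instead of the offset value 9, but its nominal day is only 15. In Tables 3-5 and 3-6 the first window carries a visit whose nominal day is 197.

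Four further points stand and limit the concern:

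- A later on-treatment record displaces the early one.
- Films on On-Filgotinib Days 1 to 15 remain Week 24 under Table 3-6.
- The 12-week waiver removes most early films.
- Subjects who stop drug for loss of response stay in the study (Protocol 3.2), so that stop alone does not trigger an early-termination lipid draw.

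**Conclusion.** The mismatch is real and confined to the Week 52 rows for mTSS and lipids, on Study Days 184 to 267 and 170 to 267 respectively, assuming a switch on Study Day 169. It reaches the Week 52 comparisons of continuous with switch groups on mTSS and non-progression, and the descriptive lipid summaries. The effect is likely small. It cannot be sized, because the documents do not say how many switchers leave in these intervals.

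A reader might infer more than the documents support:

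- *Early-exit data enter Week 52 in the switch groups alone.* This is true only up to Study Day 267. Later early exits enter it in all arms.
- *Every switcher table has the fault at Week 52.* In Tables 3-8 and 3-10 the Week 52 limit of 142 equals Study Day 310, as in Tables 3-7 and 3-9. Only their Week 36 rows open early (On-Filgotinib Day 2, against Study Day 212), and no planned test uses those rows for the switch groups.
- *The lipid rise is understated by a calculable amount.* That needs exit rates the documents do not give. Protocol 1.2.3 also reports lipids plateauing after Week 4, or after Week 8 in the 200 mg daily groups, so exits after about On-Filgotinib Day 57 (8 × 7 + 1) would be expected near plateau.
- *A confirmatory result is at risk.* The hierarchy in SAP 3.5 uses Week 12 and Week 24 only.

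**What to change.** In Tables 3-5 and 3-6, set the switchers' Week 52 lower limit to On-Filgotinib Day 100 (Study Day 268 for a switch on Day 169; the aligned value would be 103 or 97 for a switch on Day 166 or 172). Show post-switch on-treatment records before Day 100 in a listing or in a separate early post-switch row, so that no safety lipid values are lost. Aligning the descriptive Week 36 rows of Tables 3-8 and 3-10 to On-Filgotinib Day 44 (212 − 168) is optional.

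The cost is two table cells and one listing or row. The downside is that a few early-exit values leave the Week 52 rows of the switch groups.
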